1 STUDY SYNOPSIS

Study Name	Randomized Comparison between iLux™ and LipiFlow® in the Treatment of Meibomian Gland Dysfunction
Design	
 Randomized, open-label, multisite trial comparing the iLux System to LipiFlow Thermal Pulsation System to test for non-inferiority 142 subjects (284 eyes), 128 required for analysis (256 eyes) at ≥ 7 clinical sites
Objective	Determine the safety and effectiveness of the iLux System in adults with meibomian gland dysfunction (MGD)
Co-Primary Effectiveness Endpoints	Changes from baseline to the 4-week exam in Meibomian Gland Score (MGS), as assessed by a masked rater, and Tear Break-Up Time (TBUT)
Secondary Effectiveness Endpoint	Change from baseline in subject symptoms using Ocular Surface Disease Index (OSDI) at 4-week exam
Primary Safety Endpoint	Comparison of the incidence of device-related adverse events (e.g., changes in the lid margin, development of floppy eyelids, entropion or ectropion; and lash integrity) for the two treatments
Secondary Safety Endpoint	
 The evaluation of discomfort and pain during treatment Changes from baseline following treatment for the test and control devices for the following assessments: 
 Ocular Surface Staining Intraocular Pressure Best Spectacle Corrected Visual Acuity (BSCVA)
Population	Adult patients with symptoms of evaporative dry eye/MGD
Inclusion Criteria	
 Age 18 years and older of any gender or race Written informed consent to participate in the study Willingness and ability to return for all study visits Positive history of self-reported dry eye symptoms for three months prior to the study using OSDI with a score of ≥ 23 at the baseline visit Evidence of meibomian gland (MG) obstruction, based on total MGS of ≤12 in lower eyelids for each eye as assessed by a clinician not involved in the study procedure Tear break-up time <10 seconds Agreement/ability to abstain from dry eye/MGD medications for the time between the screening visit and the final study visit (ocular lubricants are allowed if no changes are made during the study)
Exclusion Criteria	
 History of ocular or corneal surgery including intraocular, oculo-plastic, corneal or refractive surgery within 1 year Subjects with giant papillary conjunctivitis Subject with punctal plugs or who have had punctal cautery Ocular injury or trauma, chemical burns, or limbal stem cell deficiency within 3 months of the baseline examination Active ocular herpes zoster or simplex of eye or eyelid or a history of these within the last 3 months Subjects who are aphakic Cicatricial lid margin disease identified via slit lamp examination, including pemphigoid, symblepharon, etc. Active ocular infection Active ocular inflammation or history of chronic, recurrent ocular inflammation within prior 3 months Ocular surface abnormality that may compromise corneal integrity Lid surface abnormalities that affect lid function in either eye

	
 • Anterior blepharitis (staphylococcal, demodex or seborrheic grade 3 or 4) • Systemic disease conditions that cause dry eye • Unwillingness to abstain from systemic medications known to cause dryness for the study duration • Women who are pregnant, nursing, or not utilizing adequate birth control measures • Individuals who have either changed the dosing of systemic medications or non-dry eye/MGD ophthalmic medications within the past 30 days prior to screening • Individuals who are unable or unwilling to remain on a stable dosing regimen for the duration of the study • Individuals using isotretinoin (Accutane) within 1 year, cyclosporine-A (Restasis) or lifitegrast ophthalmic solution 5% (Xiidra) within 3 months, or any other dry eye or MGD medications within 2 weeks of screening (ocular lubricants are allowed if no changes are made during the study) • Individuals wearing contact lenses at any time during the prior three months or during the study period • Eyelid tattoos, including permanent eyeliner makeup • Individuals that were treated with LipiFlow in either eye in the last 24 months • Individuals using another ophthalmic investigational device or agent within 30 days of study participation • Individuals who are unable to complete the required patient questionnaires in English

Clinical Sites
	
 • Dishler Laser Institute, Greenwood Village, CO • Tauber Eye Center, Kansas City, MO • Gordon Schanzlin New Vision Eye Institute, La Jolla, CA • Eyecare Consultants – Vision Source, Engelwood, CO • Barnet-Dulany-Perkins Eye Center, Phoenix, AZ • Schwartz Laser Eye Center, Scottsdale, AZ • Pepose Vision Institute, Chesterfield, MO • Other sites TBD

Procedure
	
Treatment of eyes per Instructions for Use (IFU) for the device to which the subject was randomized

Statistical Analysis
	
Categorical or binary endpoints will be summarized by count and percentage. Analysis of covariance (ANCOVA) will be used to assess the treatment effect between baseline and 4 weeks for iLux and LipiFlow treatments for the primary and secondary effectiveness endpoints. For each endpoint analyzed, the baseline value will be used as a covariate. Given that non-inferiority is demonstrated for the iLux endpoints, success will not be claimed unless the mean change from baseline in the test arm is clinically significant and significantly different from zero.

Schedule of Evaluations
	
Screening (Day -7 to Day 0)
 
 • Informed Consent • Demographics/medical/ocular history • Concomitant systemic and ophthalmic meds <hr/> 
Pre-Treatment/Baseline (Day 0)
 
 • Pain and Discomfort Questionnaires (self-assessed after treatment but prior to any clinical assessment) • OSDI • Uncorrected visual acuity • Keratometry • Manifest refraction • BSCVA • Slit Lamp for Anterior Segment Health

	
 • Lid Margin Abnormalities • Eyelid Margin Assessment (including development of entropion or ectropion, floppy eyelids, lash integrity assessment) • TBUT • Corneal Fluorescein Staining Slit Lamp Evaluation • Meibomian Gland Assessment and Scoring (must be performed by a masked rater) • Intraocular pressure 
Treatment (Day 0)
 
 • Treatment with assigned device per IFU • Assessment for adverse events 
Post-Treatment (Day 0)
 
 • Pain and Discomfort questionnaires • BSCVA • Uncorrected visual acuity • Slit Lamp for Anterior Segment Health • Lid Margin Abnormalities • Eyelid Margin Assessment • Corneal Fluorescein Staining Slit Lamp Evaluation • Intraocular Pressure • Assessment for Adverse Events one hour following treatment, including changes to eyelid margins (development of entropion or ectropion, floppy eyelids, lash integrity assessment)
	
1-Day (Day 0-1) Office Visit Follow-Up
 
 • Pain and Discomfort Questionnaires (self-assessed prior to clinical assessment) • Uncorrected visual acuity • BSCVA • Slit Lamp for Anterior Segment Health • Lid Margin Abnormalities • Eyelid Margin Assessment (including development of entropion or ectropion, floppy eyelids, lash integrity assessment) • Corneal Fluorescein Staining Slit Lamp Evaluation • Assessment for Adverse Events
	
2-Week (Day 12-16) Office Visit Follow-Up
 
 • Pain and Discomfort Questionnaires (self-assessed prior to clinical assessment) • OSDI • Uncorrected visual acuity • Keratometry • Manifest Refraction • BSCVA • Slit Lamp for Anterior Segment Health • Lid Margin Abnormalities • Eyelid Margin Assessment (including development of entropion or ectropion, floppy eyelids, lash integrity assessment) • TBUT • Corneal Fluorescein Staining Slit Lamp Evaluation • Meibomian Gland Assessment and Scoring (must be performed by a masked rater) • Intraocular Pressure • Assessment for Adverse Events
	
4-Week (Day 21-35) Office Visit Follow-Up
 
 • Pain and Discomfort Questionnaires (self-assessed prior to clinical assessment) • OSDI • Concomitant systemic and ophthalmic meds • Uncorrected visual acuity

	
• Keratometry• Manifest Refraction• BSCVA• Slit Lamp for Anterior Segment Health• Lid Margin Abnormalities• Eyelid Margin Assessment (including development of entropion or ectropion, floppy eyelids, lash integrity assessment)• TBUT• Corneal Fluorescein Staining Slit Lamp Evaluation• Meibomian Gland Assessment and Scoring (must be performed by a masked rater)• Intraocular Pressure• Assessment for Adverse Events
--	-------------------------------------------------------------------------------------------------------------------------------------------------------------------------------------------------------------------------------------------------------------------------------------------------------------------------------------------------------------------------------------------------------------------------------------------------------------------------------------------------------------------------------------------------------------------------

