4.4 Outcome Measures

4.4.1 Co-Primary Effectiveness Endpoints

The co-primary effectiveness endpoints are the changes from baseline to the 4-week exam in total Meibomian Gland Score (MGS) and Tear Break-Up Time (TBUT). MGS must be assessed by a masked

¹ "Information Sheet Guidance for IRBs, Clinical Investigators, and Sponsors Significant Risk and Nonsignificant Risk Medical Device Studies", FDA CDRH, January 2006.

rater. Clinical and statistically significant improvements from baseline for each parameter are required to achieve success for these co-primary endpoints.

The MGS is determined for the lower eyelids using a device that applies a standardized pressure to an area including 5 glands (Meibomian Gland Evaluator, Model MGE-1000, TearScience, Inc.) while viewing the eyelid margin using a slit lamp microscope to determine the presence and quality of the gland secretions. A total of 15 glands in three lower eyelid zones (nasal, medial, temporal) will be evaluated. Each gland is graded from 0 to 3 (0 = no secretion, 1 = inspissated, 2 = cloudy, 3 = clear liquid). The maximum MGS score is 45 in each eye. This endpoint has been used in previous studies evaluating the LipiFlow device [5, 6]. The clinician performing the MGS must not be involved in the study procedure and must be blinded to which arm of the study the subject is randomized.

TBUT is evaluated using the fluorescein method [4]. This measurement provides an aggregate assessment of the effectiveness of treatments to both the lower and upper eyelids.

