Lid Margin Abnormalities	Scored 0-4 based on the number of the following present in each eye: 
 • irregular lid margin • vascular engorgement • plugged meibomian gland orifices • anterior or posterior replacement of the mucocutaneous junction
Eyelid Margin Assessment	Development of any of the following: 
 • entropion or ectropion • floppy eyelids • loss of lash integrity

Assessment	Description
Tear Break-Up time	
 • Use AMCON 0.12mg Fluorescein strips • Apply one or two drops of non-preserved saline to the impregnated paper tip. Excess fluid will automatically fall off. Shaking is neither required nor desirable. • Ask the patient to look down and in. • Gently touch the strip to the superior temporal bulbar conjunctiva for one or two seconds • Ask the patient to blink three times and open eyes naturally • Immediately measure the time between the last blink and the first appearance of a dark spot on the cornea (formation of dry area) • Time shall be recorded in seconds and shall be the average of three consecutive measurements • Repeat with a new strip for the second eye
Corneal Fluorescein Staining Slit Lamp Evaluation	
National Eye Institute (NEI) corneal grading scale evaluating five corneal regions:
 
 • superior • inferior • central • temporal • central 
Each graded on a 0-3 scale (0=normal-no staining; 1=mild-superficial stippling micropunctate staining; 2=moderate-macropunctate staining with some coalescent areas; 3=severe-numerous coalescent macropunctate areas and/or patches) [8]

Meibomian Gland Assessment and Scoring	
Note: Meibomian Gland Assessments must be made by a rater not involved in the study procedure and blinded to the arm to which the subject is randomized
 
 • Assess lower eyelids using Meibomian Gland Evaluator while viewing the eyelid margin using slit lamp microscope • Evaluate 15 glands in 3 zones (nasal, medial, temporal) • Each gland graded from 0 to 3 • Maximum MGS score=45 in each eye [5, 6]
Intraocular Pressure	Measured by a Goldmann tonometer and recorded in mmHg

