6.5 Randomization

Prior to randomization it must be determined that the subject meets all entrance criteria. This includes the completion of all screening tests to determine eligibility. The randomization schedules with subjects allocated to the iLux or control LipiFlow group in a 1:1 ratio will be prepared for each site. Each envelope will have a sequential envelope number on the outside, and contain the assigned treatment procedure inside. Before the treatment, the assigned personnel will open the lowest numbered envelope. The envelope number will be documented on the study source documents and in the EDC. Randomization will take place at the treatment visit prior to subject treatment. There are no criteria for crossover in this study, so all subjects must be treated according to the arm to which they are randomized.

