- Eyelid Margin Assessment
- TBUT
- Corneal Fluorescein Staining Slit Lamp Evaluation
- Meibomian Gland Assessment and Scoring (must be performed by a masked rater)
- Intraocular Pressure

Assessment for adverse events must include assessment for changes to eyelid margins (development of entropion or ectropion floppy eyelids, and lash integrity assessment).

6.9 4-Week Follow-Up

Subjects will undergo the same screening assessments identified in Table 1 above at the 4-week visit. Specifically, the following tests will be performed:

- Discomfort and Pain Questionnaires (self-assessed prior to clinical evaluation)
- OSDI
- Uncorrected Visual Acuity
- Keratometry
- Manifest Refraction
- BSCVA
- Slit Lamp for Anterior Segment Health
- Lid Margin Abnormalities
- Eyelid Margin Assessment
- TBUT
- Corneal Fluorescein Staining Slit Lamp Evaluation
- Meibomian Gland Assessment and Scoring (must be performed by a masked rater)
- Intraocular Pressure

Assessment for adverse events must include assessment for changes to eyelid margins (development of entropion or ectropion floppy eyelids, and lash integrity assessment).

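### TBUT is a co-primary endpoint in an open-label trial, but the plan masks only the MGS rater and never says who reads TBUT

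*Combined protocol and SAP*

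**What the plan says.** The synopsis and section 4.2 describe a randomized, open-label comparison. The synopsis defines the co-primary endpoints as "Changes from baseline to the 4-week exam in Meibomian Gland Score (MGS), as assessed by a masked rater, and Tear Break-Up Time (TBUT".

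Section 4.4.1 gives a rater rule for MGS: "The clinician performing the MGS must not be involved in the study procedure and must be blinded to which arm of the study". For TBUT the same section gives only a method: "TBUT is evaluated using the fluorescein method [4", with a remark that it reflects treatment of both lids.

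Table 1 in section 6.4 repeats the MGS rule: "Note: Meibomian Gland Assessments must be made by a rater not involved in the study procedure and blinded to the arm". Its TBUT entry specifies the strip, the instillation and the blinks, then tells the reader: "Immediately measure the time between the last blink and the first appearance of a dark spot on the cornea". It adds: "Time shall be recorded in seconds and shall be the average of three consecutive measurements". It does not say who the reader is.

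The week 2 and week 4 lists in sections 6.8 and 6.9 tag one line: "Meibomian Gland Assessment and Scoring (must be performed by a masked rater". The TBUT line has no tag. Appendix A follows the same pattern.

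On timing, section 6.5 states: "Prior to randomization it must be determined that the subject meets all entrance criteria". TBUT below 10 s is an entry criterion (section 5.1), so baseline TBUT should be read before allocation.

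**The concern.** Section 7.2.3 requires both co-primaries to succeed, so a well-protected MGS cannot make up for a biased TBUT. TBUT is a timed human judgement. Standard strips and the averaging of three readings reduce random error, but a reader's expectation can enter all three readings alike.

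The exposure lies after treatment: at week 4 for the primary analysis, and at week 2 because those values can feed the LOCF, best-case and worst-case imputations in section 7.2.7. Adjusting for a baseline read before allocation does not correct a bias that enters later, and the imputation analyses deal with absent values, not biased ones.

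Bias toward iLux raises the chance of declaring non-inferiority falsely. Bias against iLux costs power. Bias shared equally by the two arms cancels in the between-arm test. It does not cancel in the additional requirement of sections 4.4.1 and 7 that the iLux change from baseline be clinically significant and different from zero.

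**Working it through.** **1. Masking rules, place by place**

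| Place | MGS | TBUT |
|---|---|---|
| Synopsis, co-primary endpoints | masked rater | no rater stated |
| Synopsis, baseline, week 2 and week 4 lists | masked rater | no rater stated |
| Section 4.4.1 | outside the procedure, blinded | method only |
| Table 1 (6.4) | outside the procedure, blinded | technique only |
| Sections 6.8 and 6.9 | masked rater | no rater stated |
| Appendix A | masked rater | no rater stated |

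No general rule masks examiners or separates the treating operator from follow-up readings. In the synopsis the masking phrase sits between commas after MGS and before TBUT, and the other rows confirm that it belongs to MGS.

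**2. Reproducing the plan's power**

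Inputs are a margin of 2.5 s, SD 4 s and stated power 93.9% (7.2.4); 128 subjects at 1:1, so 64 per arm (4.2); and a one-tailed test (7.2.1.2). Alpha of 0.025 is written only for the secondary endpoint (7.2.4). Its use for TBUT is inferred.

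- SE = 4 × √(2/64) = 0.707 s, df = 126, critical t = 1.979.
- Power = P(T′(126, ncp = 2.5/0.707 = 3.536) > 1.979) = 93.9%, as stated.
- One-sided alpha of 0.05 would give 96.9%, which does not match. This supports 0.025.

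**3. Effect of a between-arm reading bias b on the TBUT test**

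The documents give no value for b. The sizes below are assumptions: 10%, 20% and 40% of the margin.

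- False non-inferiority (true difference −2.5 s, bias toward iLux) = P(T′(126, ncp = b/0.707) > 1.979).
- Power (true difference 0, bias against iLux) = P(T′(126, ncp = (2.5 − b)/0.707) > 1.979).

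| b (s) | False TBUT non-inferiority | TBUT power |
|---|---|---|
| 0 | 2.5% | 93.9% |
| 0.25 | 5.4% | 88.4% |
| 0.5 | 10.4% | 80.1% |
| 1.0 | 28.9% | 55.8% |

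The 2.5% error doubles at b of about 0.225 s. At b = 0.5 s the false rate is 15.3% if the SD is 3 s and 8.1% if it is 5 s.

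**4. Both co-primaries together**

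Assume MGS is truly equal and the endpoints are independent, as section 7.2.4 does, and multiply by MGS power of 0.939. For b = 0, 0.25, 0.5 and 1.0 s, joint false non-inferiority is 2.3%, 5.1%, 9.8% and 27.1%. Joint power is 88.2%, 83.1%, 75.3% and 52.4%.

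**5. Adding the change-from-baseline requirement**

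Further assumptions: SD 4 s also applies to the change, so the SE of the iLux mean is 4/√64 = 0.5 s; and clinically significant is read as an observed iLux mean change of at least 2.5 s (7.1.2). With iLux truly 2.5 s worse, the chance of passing both TBUT requirements is:

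| True LipiFlow gain | b = 0.5 s | b = 1.0 s |
|---|---|---|
| 3 s | 0.1% | 2.1% |
| 4 s | 6.3% | 24.6% |
| 5 s | 10.4% | 28.9% |

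Shared bias acts here too. If the true iLux change is 2.0 s, the chance of an observed mean of at least 2.5 s is P(Z > 0.5/0.5) = 16%. A 0.5 s optimism common to both arms makes it P(Z > 0) = 50%.

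**The case against.** The strongest objection concerns consequence. Declaring success also requires a clinically significant iLux gain, and if iLux is truly 2.5 s worse it reaches a true gain of 2.5 s only when LipiFlow gains 5 s, in patients who enter below 10 s. Step 5 bears this out: the 10.4% and 28.9% are rates of false non-inferiority on TBUT and upper ends for false TBUT success. That stands as a limit on how the figures may be read. It does not remove the problem, because the extra requirement is itself open to optimism shared by both arms.

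Second, nothing in the documents supports any particular bias, its direction, or the idea that operators will read TBUT. A site may already use the masked MGS rater, and Table 1 standardises much of the technique. This is fair and bears on likelihood. It still leaves the reader of a co-primary endpoint to each site's choice.

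Third, masking the reader does not stop an unmasked subject from naming the device. That is true, and it applies equally to MGS, where the plan judged a masked rater worthwhile. The documents give no reason to treat TBUT differently.

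**Conclusion.** The gap is real. The plan requires masking for one co-primary endpoint and is silent on the other, so a site following it exactly may have the unmasked operator read week 4 TBUT. The finding rests on the text and needs no assumed bias. Its size does: with SD 4 s, 64 per arm and one-sided 0.025, a bias of about 0.225 s toward iLux doubles the false non-inferiority rate on TBUT, and 0.5 s takes it to 10.4%. In the other direction, 0.5 s takes TBUT power to about 80%. These are illustrations and not estimates of what will happen. Because no later analysis can undo the bias and the remedy is small, the reader should be specified before post-treatment readings are taken.

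**What to change.** In section 4.4.1, Table 1, sections 6.8 and 6.9, the synopsis visit lists and Appendix A, state that TBUT at weeks 2 and 4 is read by an assessor who has no part in treatment and does not know the allocation, and that the assessor's identity is recorded. The masked MGS rater can take this on. The visit lists already place TBUT before gland assessment, and it is worth making that order explicit if one person does both. Asking subjects not to disclose their device to the assessor would help. No new masking rule is needed at baseline, provided that TBUT is read before the envelope is opened.

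The cost is a wording amendment and a few more minutes of the masked rater's time at two visits. There is no added visit, no change in sample size, and no added staff if the MGS rater reads TBUT.

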2 INTRODUCTION

Meibomian glands are located in the tarsal plate of the upper and lower eyelids, where they terminate along the interior rim (or margin) of the eyelids. These glands secrete meibum, which is a lipid-rich essential component of a healthy tear film. When sufficient meibum is not present in the tear film, the aqueous layer of the tear film is disrupted and readily evaporates causing irritation, redness, and inflammation of the lid margin and surrounding tissues. Meibomian Gland Dysfunction (MGD) is associated with a failure of these glands to produce adequate quantities of meibum due to atrophy, inflammation, or obstruction, and is thought to be the most common cause of evaporative dry eye disease [1].

A common clinical treatment to restore normal gland function in patients with obstructive MGD involves the application of heat and pressure therapy to the eyelids to express the meibomian gland obstruction and other material from the gland [2]. Warming the eyelid tissue softens or melts the meibum, which is known to facilitate expression using pressure.

3 DEVICE DESCRIPTION

The iLux™ System is a medical device intended for use by Eye Care Professionals (ECP) to apply localized heat and pressure therapy to a patient's eyelids. The system consists of a handheld instrument coupled to a single-use, sterile Disposable component that is positioned behind the eyelid. The iLux device allows an ECP to view the eyelid margin through a magnifier, then warm the eyelid tissue to a range of 40 to 42°C, and then apply compression to the eyelid in order to express melted meibum from obstructed glands.

3.1 iLux Indications for Use

The iLux System is indicated for the application of localized heat and pressure therapy in adult patients with chronic cystic conditions of the eyelids, including meibomian gland dysfunction (MGD), also known as evaporative dry eye.

3.2 iLux Components

The iLux system is shown in Figure 1.

Figure 1: The iLux system shown with a Disposable attached to the Instrument

3.2.1 iLux Disposable

The iLux Disposable is a sterile component used for a single patient treatment, and then disposed. The main parts of the Disposable are shown in Figure 2. During a treatment, the Inner Eyelid Pad is inserted behind the eyelid in the fornix and is intended to contact the inner mucosal lining (i.e., the palpebral conjunctiva). The Outer Pad, which opposes the Inner Pad, contacts the skin on the outer surface of the eyelid. Light produced by the Instrument is transmitted through the clear Outer Pad to warm the eyelid tissue. The Outer Pad is used to apply pressure to the eyelid by moving this component towards the Inner Pad by means of a mechanism in the Instrument. Temperature sensors in the Outer and Inner Pads monitor eyelid temperature during a treatment.

[figure not shown]

Figure 2 The main parts of the iLux Disposable are shown in this rendering. Not shown are the temperature sensors.

3.2.2 iLux Instrument

The iLux Instrument is a handheld, electronic instrument used together with the iLux Disposable to apply heating and pressure to the eyelid. The Instrument includes electronic circuits that read sensors in the Inner and Outer Eyelid Pads to measure temperatures representative of inner and outer eyelid temperature, respectively. Warming is accomplished using light energy emitted from LEDs in the Instrument. A mechanism in the Instrument allows the operator to apply pressure to the eyelid by controlling the movement of the Outer Pad using finger pressure applied to the Compression Control button. The force applied to the Compression Control is measured by a sensor in this mechanism. A graphic Screen displays information for operating the Instrument during a treatment. A magnifier allows the operator to view the eyelid margin during treatment.

Eyelid temperature is measured using sensors in the Disposable including two sensors in the Outer Pad and two in the Inner Pad. When the Disposable is attached to Instrument, spring loaded pins mounted above the Shroud make an electrical connection to the pads in the Disposable. Electronic circuitry in the Instrument reads the sensors and determines temperatures more than 20 times a second. The accuracy of the temperature measurement system is ± 1 °C. The circuitry performs self-test checks to ensure the sensors are operating properly. If the electronics detect a failure, an error code is displayed and the heat source is disabled.

The Instrument features an integrated Display Screen shown in Figure 3. The Display Screen shows the elapsed warming time that the temperature is above 38 °C (in seconds), the compression force applied by the user, the highest of the two temperature sensors located in the Inner Eyelid Pad, and status of the rechargeable batteries as indicated by a battery icon. The Display also provides messages regarding status or conditions that require the operator's attention.

[figure not shown]

Figure 3: The information displayed on the screen. Any operating message is displayed on the bottom row.

Pressure applied to the eyelid is controlled by the ECP depressing the Compression Control button using their thumb or finger, which causes the Outer Pad to move towards the opposing Inner Pad. The mechanism that connects the Compression Control button to the Outer Eyelid Pad is shown in Figure 4. When the Disposable is attached to the Instrument, the Outer Eyelid Pad automatically attaches to the front of the Shroud. The Compression Control button is connected to the movable Shroud by a linkage, which reduces the force applied to the Compression Control button by at least 50%. The ECP can retract or advance the Outer Eyelid Pad and Shroud combination as well as control the amount of pressure applied using the Compression Control button. A sensor is mounted in this mechanism to measure the force applied by the user to Compression Control button. Electronic circuitry monitors the sensor output and then displays the compression force on the Screen to provide feedback for the user during a treatment.

[figure not shown]

Figure 4 A mechanism in the Instrument allows the eye care professional to control the pressure applied to the eyelid. Depressing the Compression Control button causes the Outer Pad attached to the Instrument Shroud to advance towards the Inner Pad. A spring-return feature causes the Outer Pad and Shroud to retract when the Compression Control is released.

The eyelid tissue is warmed by light energy produced by LEDs in the Instrument and transmitted through the clear Outer Pad. The LEDs are located behind a clear window on the open end of the Shroud. Two wavelengths of light are used: lime-green (568 nm) and near-infrared (850 nm). Chromophores in the eyelid absorb the light energy and heat the surrounding tissue [3]. Similarly, chromophores in the black plastic of the Inner Pad absorb the light energy and warm nearby tissue of

the inner eyelid. A small fan, which creates an audible sound, provides cooling for the LEDs by drawing air through slotted openings in the housing.

The system is designed to protect against unintended exposure to the light. The Inner Pad and Eye Shield block light transmission directly into the eye during a treatment. The Instrument is designed to prevent heat source operation without a Disposable attached. To minimize stray light, the heat source cannot be operated without the user advancing the Outer Pad to within 4 to 6 mm of the Inner Pad by depressing the Compression Control.

The top surface of the Compression Control has a Heater Control switch that is slid forward by the operator's thumb or forefinger to turn on the warming LEDs. This switch has a spring-return feature, so that when it is released, or when the ECP's thumb or forefinger is relaxed, the Heater Control switch returns to its normal "off" position. The highest temperature measured by the Inner Eyelid Pad sensors is shown on the LCD. When the heater is turned on by the ECP, circuitry adjusts power to the LEDs to raise eyelid temperatures to 40 to 42 °C. At any time during heating, if any of the measured eyelid temperatures exceeds 42 °C, the high-temperature alert symbol is displayed and the light source is dimmed. If any one of the temperatures exceeds 44 °C, the attention required symbol is displayed the Instrument automatically turns off the light source until the temperature drops below 40 °C. The elapsed time that the tissue is warmed above 38°C is displayed on the screen. The duration that the LEDs can be operated is limited to 90 seconds from initial activation; after this period, sliding the Heater Control switch forward will no longer turn on the LEDs. Momentarily depressing the Instrument power ON/OFF switch resets the 90 second LED timer and the elapsed warming timer.

The instrument records temperature and force along with other operating data in internal memory. Data. The performance data can be downloaded to an external computer by Tear Film for the purposes of troubleshooting or other data needs.

